### 13.2.3 Primary Analysis of the Key Secondary Endpoint of EFS

In the event that the primary endpoint OS for phase III is significant as determined by the primary analysis, then the key secondary endpoint of EFS will be formally tested hierarchically in a confirmatory setting at an overall one sided alpha of 0.025 level at the same time as the primary endpoint. Both hazard ratio and p-value for EFS will be presented.

### 13.2.4 Sensitivity Analysis

To evaluate the impact of off-protocol transplantation, sensitivity analyses will be conducted. Approaches will include but not limited to: 1) considering transplantation as a competing risk, 2) censoring patients who go off study for transplant without relapse at the time they discontinue the treatment, 3) multi-state model. In addition, the proportion of patients who received transplantation in the two arms will be summarized and compared using a chi-square test. We acknowledge that censoring patients at the time of HCT may potentially lead to informative censoring and biased efficacy results. Similar sensitivity analyses will be conducted for patients who take other off-protocol treatment due to MRD.

### 13.2.5 Subgroup Analyses

Subgroup analyses by potential prognostic factors at baseline will be conducted, to evaluate the consistency of the treatment effect among each subgroup. Non-parametric methods such as Kaplan-Meier and log-rank tests will be used within each subgroup. Univariate/multivariate Cox models will be fit within each subgroups; hazard ratios will be used to quantify the treatment effect within each subgroup, along with the 95% confidence intervals.

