### 13.1.2 Sample Size and Power Justification

#### Phase II component

Patients will be randomized to receive daunorubicin and cytarabine or the novel regimen with equal allocation using a permuted block method. E2906 study reported a 1-year EFS of 29%. Therefore, we estimate that the 1-year EFS in the daunorubicin and cytarabine arm will be 30%. We are interested in testing the alternative hypothesis that the 1-year EFS in the novel experimental arm will be at least 47% (a 17% improvement in the 1-year EFS). This translates to an improvement in the median EFS from 7 to 11 months (HR = 0.64), assuming exponential distributions of EFS in both control and experimental arm. A sample size of 131 evaluable patients per arm (262 total) provides 96% power to detect an improvement in median EFS from 7 months to 11 months (a hazard ratio of 0.64), using a one-sided log-rank test at a significance level of 10%.

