#### Phase II component

**Final analysis:** The Phase II decision-making will be conducted when at least 191 events are observed (approximately expected 37 months after the first patient enrolled). If less than 191 events are observed 2 years after Phase II accrual ends, then the Phase II decision will occur at the target data lock.

At the final analysis of the Phase II, it will be concluded that the experimental arm regimen is promising, if we a one-sided p-value  $< 0.10$  from the log-rank test favoring the experimental arm.

*As of Amendment 04, there will be no additional accrual to the Phase III component of the trial regardless of the outcome of the Phase II analysis. Given the maturity of follow-up on the current patients and no additional accrual to the trial, the final Phase III OS analysis will also be performed at the time of final Phase II EFS analysis. All Phase III alpha (one-sided 2.5%) will be spent at this analysis. The target data lock date is August 12, 2024.*

**Interim analysis:** We will conduct a futility interim analysis which will take place after 50% of the total events have occurred (approximately 25 months after the first patient enrolled). If at the planned interim analysis the hazard ratio is  $>1.0$  in favor of the control arm, the recommendation will be to stop further accrual to the experimental arm and conclude that the novel regimen does not have improved EFS.

We will suspend accrual between phase II and III. In order to protect the phase III comparison, the results of the phase II portion will only be released to the FDA and/or industry sponsors for regulatory purposes, contingent upon the approval and recommendation from the Alliance Data Monitoring Committee. Other than that, the Alliance DMC will only release whether the criteria for continuation to Phase III have been satisfied and not any of the actual results.

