#### Phase III component

The final analysis will be conducted after 521 deaths have been observed. In addition, we will conduct 2 interim analyses which will take place after approximately 50% and 75% of the total events have occurred. The first interim analysis is for futility only, and the second interim for both futility and efficacy. If in the second interim evaluation, sufficient evidence (per criteria outlined below) is observed that the experimental arm is superior to the control arm in terms of OS, then accrual to the control arm may be suspended and terminated. To preserve the Type I error rate control on superiority, the Lan-DeMets error spending function with the O'Brien-Fleming stopping boundaries is utilized. Futility boundaries

have also been developed for the comparison against control, where if at any of the planned interim analyses the hazard ratio is  $>1$  in favor of the control arm, the recommendation will be to stop further accrual to the experimental arm (if the trial is still accruing) and conclude that the novel regimen does not have improved OS. At the final analysis, if we observe a p-value  $\leq 0.022$  from the log-rank test (equivalently,  $HR \leq 0.838$  favoring the experimental regimen, assuming the exponential distribution) we will conclude that the novel regimen significantly improves the OS, compared to the daunorubicin and cytarabine arm. The interim and final analysis boundaries and characteristics were generated using the East clinical trial software program (version 6.3, Cytel Inc).

Information Fraction	Cum. events	Cum. alpha spent	Cum. beta spent	Efficacy Boundaries			Futility Boundaries	
				HR	P-value	Z score	HR	p-value
50%	261	0	0.01	NA	NA	NA	1	0.5
75%	391	0.010	0.011	0.789	0.010	-2.339	1	0.5
100%	521	0.025	0.1	0.838	0.022	-2.012	0.838	0.022

As of Amendment 04, there will be no additional accrual to the Phase III component of the trial regardless of the outcome of the Phase II analysis. Given the maturity of follow-up on the current patients and no additional accrual to the trial, the final Phase III OS analysis will also be performed at the time of final Phase II EFS analysis. The final Phase III of analysis of OS will conclude that the novel regimen significantly improves the OS compared to the daunorubicin and cytarabine arm if the one-sided p-value from the stratified log-rank test is  $< 0.025$ . The target data lock date is August 12, 2024.

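### The subgroup section aims to assess consistency of the treatment effect but plans no comparison between subgroups, and comparing the planned within-subgroup p-values would often make a uniform effect look inconsistent

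*Combined protocol and SAP*

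**What the plan says.** Section 13.2.5 gives the purpose of the subgroup analyses as "to evaluate the consistency of the treatment effect among each subgroup". It then names two sets of methods:

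- On curves and tests, the section states: "Non-parametric methods such as Kaplan-Meier and log-rank tests will be used within each subgroup".
- On modelling and effect size, its wording is: "Univariate/multivariate Cox models will be fit within each subgroups; hazard ratios will be used to quantify the treatment effect within each subgroup". Each such estimate comes with a 95% interval.

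The section does not list the factors, set a test level, or give a rule for calling effects consistent or inconsistent.

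Nothing elsewhere supplies a between-subgroup comparison of the treatment effect:

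- Objective 2.2.4 uses the word interaction, but its analysis (last item of Section 13.2.2) only asks whether baseline characteristics predict outcome.
- Section 13.7 says differences in treatment effect by race and gender will be looked for. It names no method, and says that no power was added for subsets.
- The one interaction that is modelled, in Section 14.3.4, is between blood and marrow measurable residual disease.

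**The concern.** Consistency is a question about the difference between subgroup effects, whereas each planned analysis estimates or tests the effect within one subgroup. A log-rank test that is significant in one level and not in the other does not show that the effects differ. Even when the effect is the same everywhere, such a split arises because each subgroup holds only part of the events and its test has limited power.

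This is a registration study, and the natural subgroups are the stratification factors: age, performance status, and de novo versus secondary or therapy-related AML. Amendment 04 ended accrual, so subgroup event counts will be modest. A reader shown separate p-values could conclude that benefit is confined to, or absent from, one of these groups when chance explains the pattern.

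**Working it through.** **Inputs from the protocol.** EFS: HR 0.64, one-sided 10% level and 96% power (Section 13.1.2), with the Phase II decision at 191 events (Section 13.2.1). OS: HR 0.75 and one-sided 2.5% (Section 13.1.2). Allocation is 1:1 (Section 13.1).

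**Assumptions, not in the documents.** The share of events in each subgroup level (50:50 to 80:20), and the number of deaths at the OS analysis (160 to 220). The 521 deaths of the Phase III design cannot be reached in a Phase II cohort planned at 262 patients.

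**1. Reproduce the plan's figure.** Log-rank power with D events and 1:1 allocation is Φ(|ln HR| × √D / 2 − z). For EFS: 0.4463 × √191 / 2 = 3.084, and 3.084 − 1.282 = 1.802, so power is 0.964. The plan states 96%.

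**2. Power within one subgroup, uniform HR 0.64.** A 50:50 split leaves 95.5 events per level: 0.4463 × √95.5 / 2 = 2.181.

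- One-sided 0.025, which matches the planned 95% intervals: Φ(2.181 − 1.960) = 0.587.
- One-sided 0.10, the Phase II level: Φ(2.181 − 1.282) = 0.816.

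**3. Chance that exactly one of two levels is significant.** The levels share no patients, so the chance is p1(1 − p2) + p2(1 − p1). For 50:50 at one-sided 0.025: 2 × 0.587 × 0.413 = 0.485.

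| Assumed split of 191 EFS events | Power per level, one-sided 0.025 | Exactly one significant, 0.025 | Exactly one significant, 0.10 |
|---|---|---|---|
| 50:50 | 0.587, 0.587 | 48% | 30% |
| 70:30 | 0.732, 0.393 | 55% | 37% |
| 80:20 | 0.788, 0.281 | 63% | 47% |

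**4. The same for OS, uniform HR 0.75, one-sided 0.025, 50:50.**

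- 160 deaths: power per level 0.250, so 2 × 0.250 × 0.750 = 0.375.
- 220 deaths: power per level 0.326, so 2 × 0.326 × 0.674 = 0.439.

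**5. What an interaction test does.** At two-sided 0.05 it flags a truly uniform effect 5% of the time per factor. Over three independent factors, at least one is flagged 1 − 0.95³ = 14% of the time.

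Its power is low. With D events split 50:50, the variance of the log ratio of HRs is 4/(D/2) + 4/(D/2) = 16/D. With 191 events the standard error is √(16/191) = 0.289. The ratio detectable with 80% power is exp(−(1.960 + 0.842) × 0.289) = 0.44. For a true ratio of 0.6, power is Φ(0.511/0.289 − 1.960) = 0.42.

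**6. What the planned intervals show.** Under a uniform effect and a 50:50 split, two subgroup 95% intervals fail to overlap only when the standardised difference exceeds 1.96 × 2/√2 = 2.77, which happens about 0.6% of the time.

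**The case against.** The strongest reply is that the plan does not say consistency will be judged by which subgroups reach significance. It sets no subgroup level and no decision rule, and it reports HRs with 95% intervals, which is estimation. Step 6 shows that those intervals will rarely be disjoint under a uniform effect. Because the levels are disjoint, a reader can also derive the ratio of HRs and its interval from the planned univariate subgroup results. It would therefore go too far to infer that the section cannot answer its own question, or that the planned output as a whole will usually mislead.

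This stands, and it limits the percentages in steps 3 and 4 to one use of the output: comparing p-values across subgroups. It does not remove the point. The plan prescribes those within-subgroup tests, gives no guard against comparing them, and leaves the direct comparison to the reader. Non-overlap of intervals is also a conservative criterion and does not make the plan adequate.

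Two further replies are fair. The test level is a choice, and at one-sided 0.10 the 50:50 figure for EFS is 30%, not 48%. And an interaction test on 191 events is weak, so adding one cannot establish consistency.

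**Conclusion.** The point holds as a mismatch between aim and method in a supportive analysis: consistency is the stated aim, and no between-subgroup comparison is specified. If within-subgroup p-values are compared, a uniform EFS effect of HR 0.64 gives a split result about 48% of the time at one-sided 0.025 (about 30% at one-sided 0.10) with 191 events divided 50:50, and more often with unequal splits. For OS at HR 0.75 and 160 to 220 deaths the figure is about 38% to 44%. The splits and the death counts are assumptions.

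A reader might infer that the trial's conclusions are at risk, or that the plan intends claims limited to a subgroup. The documents support neither. The decisions rest on the overall EFS and OS tests and the hierarchical EFS test (Sections 13.2.1 and 13.2.3), and no claim or error allocation is tied to subgroup results. The change is worth making because it is cheap and closes off a likely misreading.

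**What to change.** Amend Section 13.2.5 as follows:

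- For each baseline factor, fit one Cox model in all randomised patients with treatment, factor and treatment-by-factor interaction, stratified by the other randomisation factors.
- Report the ratio of HRs with its 95% interval, and the interaction p-value, beside the forest plot of subgroup HRs.
- State that within-subgroup log-rank p-values will not be used to judge consistency.
- State that these analyses are exploratory, unadjusted for multiplicity and low in power, so a non-significant interaction does not establish consistency.

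The cost is a short text change and minor programming, with no new data and no effect on the primary analyses. The intervals for the ratio of HRs will be wide. The text should be settled before the release of outcome data described in Section 13.5; if that has already happened, the report should say that the comparison was specified afterwards.

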## 13.3 Accrual Time and Study Duration

The anticipated accrual rate is approximately 5 pts/month in the first year, 10 pts/month second year, and 14 patients per month afterwards. The phase II component is expected to accrue in 30 months after trial activation. Accrual will be suspended between the phase II and phase III component for primary endpoint analysis from phase II; the suspension between the Phase II and Phase III is expected to be 12 months to allow for follow-up on the last phase II patients and completion of the primary analysis for phase II. The phase III component is expected to accrue in approximately 59 months. Including the suspension between Phase II and III, the total

study duration is expected to be approximately 83 months, or until the last Phase III patient accrued has been observed for at least 12 months.

*As of Amendment 04, there will be no additional accrual to the Phase III component of the trial regardless of the outcome of the Phase II analysis.*

#### **13.4 Adverse Event Stopping Rule**

Early stopping rule will be based on 30-day mortality rate. If 3 or more of the first 20 Phase II patients enrolled or 15% or more of the Phase II patients enrolled thereafter die within 30 days after start of treatment, enrollment to the study will be suspended. The study team will review all adverse event data in light of the early deaths. A trial recommendation will be formulated and presented to the Alliance DSMB – the study may permanently close or may re-open to accrual after any needed modifications to the dose, the design etc., and after discussion with CTEP.

#### **13.5 Study Monitoring**

As a randomized phase II/III trial this study will be monitored by the Alliance Data and Safety Monitoring Board (DSMB) twice per year. The DSMB follows the Alliance Policies and Procedures for all randomized phase II trials. The DSMB will review accrual, toxicity, and interim analyses results. All summary findings of the DSMB will be communicated to study investigators by the Alliance. In addition the Alliance Statistical Data Center will submit quarterly reports to CTEP by electronic means using the Clinical Data Update System.

*All EFS and OS outcome data will be requested for release after DSMB review at the time of the final Phase II EFS analysis, with patient follow-up continuing per protocol.*

#### **13.6 Clinical Data Update System (CDUS) Reporting**

This study will be monitored by the Clinical Data Update System (CDUS) Version 3.0. Cumulative protocol- and patient-specific CDUS data will be submitted electronically to CTEP on a quarterly basis by FTP burst of data. Reports are due January 31, April 30, July 31, and October 31. Instructions for submitting data using the CDUS can be found on the CTEP Web site (<http://ctep.cancer.gov/reporting/cdus.html>).

**Note:** If your study has been assigned to CDUS-Complete reporting, **all** adverse events (both routine and expedited) that have occurred on the study and meet the mandatory CDUS reporting guidelines must be reported via the monitoring method identified above. If your study has been assigned to CDUS-Abbreviated reporting, no adverse event reporting (routine or expedited) is required to be reported via CDUS, but expedited adverse events are still required to be submitted via CTEP-AERS.

### 13.7 Inclusion of Women and Minorities

NIH policy requires that women and members of minority groups and their subpopulations be included in all NIH-supported biomedical and behavioral research projects involving NIH-defined clinical research unless a clear and compelling rationale and justification establishes to the satisfaction of the funding Institute & Center (IC) Director that inclusion is inappropriate with respect to the health of the subjects or the purpose of the research. Exclusion under other circumstances must be designated by the Director, NIH, upon the recommendation of an IC Director based on a compelling rationale and justification. Cost is not an acceptable reason for exclusion except when the study would duplicate data from other sources. Women of childbearing potential should not be routinely excluded from participation in clinical research. Please see <http://grants.nih.gov/grants/funding/phs398/phs398.pdf>.

This study will be available to all eligible patients, regardless of race, gender, or ethnic origin. There is no information currently available regarding differential effects of this regimen in subsets defined by race, gender, or ethnicity, and there is no reason to expect such differences to exist. Therefore, although the planned analysis will, as always, look for differences in treatment effect based on racial and gender groupings, the sample size is not increased in order to provide additional power for subset analyses.

The geographical region served by the Alliance, has a population which includes approximately 18% minorities. Based on prior Alliance studies involving similar disease sites, we expect about 18% of patients will be classified as minorities by race and about 40% of patients will be women. Expected sizes of racial by gender subsets for patients registered randomized to this study are shown in the following table.

DOMESTIC PLANNED ENROLLMENT REPORT						
Racial Categories	Ethnic Categories				Total	
	Not Hispanic or Latino		Hispanic or Latino			
	Female	Male	Female	Male		
American Indian/ Alaska Native	6	2	2	6	16	
Asian	8	15	2	2	27	
Native Hawaiian or Other Pacific Islander	2	4	2	2	10	
Black or African American	30	38	2	0	70	
White	186	282	29	50	547	
More Than One Race	0	0	0	0	0	
Total	232	341	37	60	670	

### 14.0 CORRELATIVE AND COMPANION STUDIES

There will be three substudies within A041701. Cytogenetics ([Section 14.1](#)) and Molecular Genetic Analysis ([Section 14.2](#)) are required for all patients. A041701-LC1 ([Section 14.3](#)) is an integrated substudy and patients are encouraged to participate.

## 14.1 Cytogenetic Correlative Science (Alliance A041701)

### 14.1.1 Background

Cytogenetic analyses in acute myeloid leukemia (AML) and acute lymphoblastic leukemia (ALL) have revealed a great number of non-random chromosome abnormalities. In many instances, molecular studies of these abnormalities identified specific genes implicated in the process of leukemogenesis. The more common chromosome aberrations have been associated with specific laboratory and clinical characteristics, and are now being used as diagnostic and prognostic markers guiding the clinician in selecting the most effective therapies. Specific chromosome aberrations and their molecular counterparts have been included in the World Health Organization classification of hematologic malignancies, and together with morphology, immunophenotype and clinical features are used to define distinct disease entities. The European Leukemia Net Classification also uses specific chromosome aberrations and molecular information to classify patients.

Pretreatment cytogenetic findings have been repeatedly shown to be among the most important, independent prognostic factors in AML. Consequently, cytogenetic analyses are considered mandatory for analyzing outcome of many clinical trials and are currently used to stratify patients for different types of therapy. For instance, based on the European Leukemia Net (ELN) 2017 risk categories (Döhner et al, Blood, 2017; 129:424-47), patients with inv(16)(p13.1q22) or t(16;16)(p13.1;q22) and t(8;21)(q22;q22.1) are associated with a better risk and survival. Patients with t(6;9)(p23;q34.1), t(v;11q23.3), t(9;22)(q34.1;q11.2), inv(3)(q21.3q26.2) or t(3;3)(q21.3;q26.2), -5 or del(5q), -7, -17/abn(17p) and complex or monosomal karyotype are associated with adverse risk and poor survival. The remaining patients, those with t(9;11)(p21.3;q23.3) or cytogenetic abnormalities not classified as favorable or adverse are associated with intermediate risk and survival.

Clonal chromosome abnormalities, that is, an identical structural aberration or gain of the same, structurally intact chromosome detected in at least two metaphase cells or the same chromosome missing from a minimum of three cells, are consistently found in the majority of AML patients at diagnosis. However, in contrast to patients diagnosed with CML, who are invariably positive for t(9;22) or its variants, the cytogenetic picture of AML is much more complex. To date, approximately 200 different structural and numerical aberrations such as reciprocal translocations, inversions, insertions, deletions, unbalanced translocations, isochromosomes, isodicentric chromosomes, isolated trisomies and monosomies have been found to be recurring chromosome changes in AML. Many of these aberrations are very rare, being so far detected in a few patients worldwide, whereas others occur more frequently [25].

### 14.1.2 Objectives

- Correlate specific karyotype groups (normal or various primary and secondary chromosomal abnormalities) with clinical and laboratory parameters.
- Correlate specific karyotype groups with response rates, response duration, survival and cure in patients treated with various induction and post-induction regimens.
- Correlate specific karyotype groups with selected molecular abnormalities.
- To correlate specific karyotype groups with measurable residual disease.
- To correlate CR karyotype with outcome.

- To determine karyotype changes at end of consolidation and the influence of the type of change (or no change) in karyotype at end of consolidation on subsequent clinical course.
- To determine karyotype changes at relapse and the influence of the type of change (or no change) in karyotype at relapse on subsequent clinical course.

